7.5 Questionnaire Administration

According to the inclusion criteria, eligible participants will be identified from their responses to the network's Enrollment Questionnaire.

Consistent with regulations outlined by the University of Alabama (UAB) IRB and any regional/local IRBs, information about the study will be provided to all eligible participants via an information sheet/questionnaire link in the email invitation. Completion of the questionnaire will indicate tacit consent.

After the invitation and two follow-up email reminders, the NCC will provide the Node Coordinators (NCs) with a list of non-responders and incomplete responders. The NCs will systematically contact non-responders and incomplete responders to encourage survey completion by email, phone, or fax.

If no feedback is received or the participant does not complete the questionnaire after multiple follow-up attempts over a period of up to three months, it is assumed the practitioner is not interested in the study. Node Coordinators may also contact participants as part of data cleaning conducted by the NCC.

8 ASSESSMENT OF SAFETY

8.1 Definitions of Safety Parameters

8.1.1 Unanticipated Problems

The Office for Human Research Protections (OHRP) considers unanticipated problems involving risks to subjects or others to include, in general, any incident, experience, or outcome that meets all of the following criteria:

- Unexpected in terms of nature, severity, or frequency given (a) the research procedures that are described in the protocol-related documents, such as the IRB-approved research protocol and informed consent document; and (b) the characteristics of the subject population being studied;
- Related or possibly related to participation in the research (possibly related means there is a reasonable possibility that the incident, experience, or outcome may have been caused by the procedures involved in the research); and
- Suggests that the research places subjects or others at a greater risk of harm (including physical, psychological, economic, or social harm) than was previously known or recognized.

8.2 Specification of Safety Parameters

Safety monitoring for this study will focus on unanticipated problems involving risks to participants.

8.3 Reporting Procedures

8.3.1 Unanticipated Problem Reporting

Per National Dental PBRN procedures, unanticipated incidents and events will be reported to the PI. After the PI is made aware of the incident/event, the following procedures will be followed.

Incidents or events that meet the OHRP criteria for unanticipated problems require the creation and completion of an unanticipated problem report form. OHRP recommends that investigators include the following information when reporting an adverse event, or any other incident, experience, or outcome as an unanticipated problem to the IRB:

- Appropriate identifying information for the research protocol, such as the title, investigator's name, and the IRB project number;
- A detailed description of the adverse event, incident, experience, or outcome;

- An explanation of the basis for determining that the adverse event, incident, experience, or outcome represents an unanticipated problem;
- A description of any changes to the protocol or other corrective actions that have been taken or are proposed in response to the unanticipated problem.

To satisfy the requirement for prompt reporting, unanticipated problems will be reported using the following timeline:

- Unanticipated problem will be reported to the IRB as soon as possible but in all cases within 10 working days of the investigator becoming aware of the problem.
- All unanticipated problems should be reported to appropriate institutional officials (as required by an institution's written reporting procedures), the supporting agency head (or designee), and OHRP within one month of the IRB's receipt of the report of the problem from the investigator.

All unanticipated problems will be reported to NIDCR concurrently with reporting to the IRB. These reports will be made to NIDCR's centralized reporting system via the Clinical Research Operations and Management Support (CROMS) contractor:

- Product Safety Fax Line (US): [name]
- Product Safety Fax Line (International): [contact]
- Product Safety Email: [contact]

9 STUDY OVERSIGHT

The PI will be responsible for study oversight, including monitoring safety, ensuring that the study is conducted according to the protocol and ensuring data integrity. The NCC will provide the PI with current data reports, and the PI will review the data for safety concerns and data trends at regular intervals, and will report to the IRB and NIDCR any Unanticipated Problem (UP) or any other significant event that arises during the conduct of the study, per the IRB's reporting time-frame requirements. To ensure data integrity, the PI, NCC, and study team will adhere to quality management processes (see Section 13).

Document Owner: Study PI

TOP-AC-Protocol-2021-04-19 V1.0

10 CLINICAL SITE MONITORING

No outside clinical site monitoring will be employed for this study. The NCC is responsible for launching the study and collecting data received as part of the study. Quality Assurance/Quality Control activities associated with data collection and processing will be outlined in the Data and Quality Management Plan (DQMP). The NCC will ensure that the quality and integrity of the study data and data collection are maintained. The NIDCR reserves the right to conduct independent clinical site monitoring as necessary.

Document Owner: Study PI

TOP-AC-Protocol-2021-04-19 V1.0

11 STATISTICAL CONSIDERATIONS

11.1 Study Objectives and Research Questions

This is a cross-sectional questionnaire to assess general dentists' current understanding and approach to medical management of patients taking anticoagulants and planning to undergo dental procedures associated with a bleeding risk. As such, formal hypothesis testing will not be conducted to achieve the study objectives.

Below are the objectives and the research questions:

11.1.1 Primary Objective:

1. To describe general dentists' approach to managing dental treatment for patients taking conventional ACs and DOACs.

Research Questions:

- What is the frequency with which ACs/DOACs are stopped for a dental procedure that is associated with bleeding?
- Among those who stop ACs/DOACs, how long prior to dental procedures with risk for bleeding does the dentist/physician act to discontinue ACs/ DOACs?
- What is the frequency with which the dentist makes his/her own decision, suggests to the patient's physician how to act, or defers to the physician's decision regarding discontinuing ACs or DOACs?
- What is the frequency with which dentists use laboratory tests to guide their approach towards patients taking ACs or DOACs?
- What post-procedure practices are in use when the dentist provides treatment associated with bleeding risk for patients taking ACs or DOACs?
- What is the frequency with which practitioners prefer to refer patients taking ACs/DOACs to another dental office?
- What is the level of practitioners' comfort in treating patients on ACs/DOACs?

11.1.2 Secondary Objective:

 To examine the associations between stopping ACs/DOACS prior to a dental procedure that causes bleeding (and, if so, when) and practitioner/practice characteristics.

Research Questions:

What are the associations between stopping ACs/DOACs prior to a dental procedure that causes bleeding and each of the following variables (and, if so, when) -

- The practice's region (6 National Dental PBRN regions).
- The practice's location (urban or suburban vs rural).
- How long ago the dentist graduated from dental school.
- Whether the dentist completed a general dentistry residency (AEGD or GPR or not).
- Experience with treating patients on ACs/DOACs.
- 2. To describe how general dentists classify the severity of post-operative bleeding.
 - Classification of intra-oral bleeding scenarios after a simple extraction (minor, moderate, or major).

11.2 Sample Size Considerations

11.2.1 Sample size calculation details:

- 1) Generate point estimates with good precision (narrow confidence intervals) of proportions or means for survey items (Primary Objective and Secondary Objective 2). A sample size of 825 would allow us to construct two-sided 95% Cls of width ±3.47% (i.e., margin of error) for a binary item with proportion of .50. For items assuming an approximately interval scale (e.g., Likert-type items) and a standard deviation of 1, a sample size of 825 would allow us to construct two-sided 95% Cls of width ±0.068.
- 2) Statistically test for bivariate relationships described in the final analysis plan for Secondary Objective 1. With a sample size of 825, we will have 80% power to detect multiple correlations (R) as small as .10 in a linear regression at a two-tailed alpha level of .05. For the analyses involving logistic regression, we will have 80% power to detect an odds ratio as large as 1.48 (or 0.67 in the opposite direction), assuming a 50% split on a binary independent variable and 50% rate in the outcome for the reference group and an odds ratio as large as 1.22 (0.82 in the opposite direction) for a one standard deviation unit change in a continuous independent variable at a two-tailed alpha level of .05.

11.2.2 Overall summary of sample size estimations:

To achieve a sample size of 825, 1650 Network clinically active dentists will be invited to participate; this assumes a conservative completion rate of 50% based on prior National Dental PBRN participation rates.

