11.3 Final Analysis Plan

We will examine the distribution of all variables prior to analyses and verify all missing and out-of-range values. We will evaluate all inferential analyses at an alpha level of .05.

For the primary objective and secondary objective 2, we will use descriptive statistics for each of the items in the questionnaire and vignettes. Descriptive statistics will also be used for analysis for each of the practitioner and practice descriptors in the network's Enrollment Questionnaire database. We will also calculate confidence intervals around proportions for categorical items and around means for interval level items.

For secondary objective 1, we will use logistic regression for binary outcomes (items 11.I, 13.I, 14.I, 15.I, 16.I, and Vi1.7 & V1.8 [option a vs b-d]), ordinal logistic regression for ordinal outcomes (Vi1.7 & V1.8 [option b vs c vs d]), and linear regression for the reasonably continuous outcomes (2.IV, 3.IV, 7.IV, 8IV). For each regression analysis, we will test the following independent variables separately: practice region (categorical with six levels representing each PBRN region), practice location (binary with ubran/suburban vs rural), duration since graduating dental school (continuous), completion of residency program type (categorical, with three levels representing AEGD vs GPR vs none), number of patients seen in the past three months taking ACs (continuous), familiarity with DOACs (continuous), and number of patients seen in the past three months taking DOACs (continuous). Categorical independent variables will be dummy coded. Also, because of the large number of tests being conducted, we will adjust for multiplicity using the Benjamini and Hochberg method.³⁷

Missing data. Data from incomplete questionnaires may be included in data analyses. Participants will be able to submit questionnaire with incomplete data as 22 % (6/27) of the questions do not require responses. Depending on the extent of missing data and available resources for analyses, the study team may consider statistically appropriate methods for imputing missing information.

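### The stated 80% power for R = .10 holds only for single-term predictors, not for region or residency, and OR 1.48 is given only for a 50/50 split that is not tied to the one binary predictor planned

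*Protocol*

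**What the plan says.** Section 11.2.1, item 2, presents its figures as the power for the bivariate tests of secondary objective 1 that the final analysis plan describes. For linear regression it says "With a sample size of 825, we will have 80% power to detect multiple correlations (R) as small as .10". The test is two-sided with alpha .05, and the number of predictor terms behind the figure is not given.

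For logistic regression it gives OR 1.48 (0.67 in the other direction), "assuming a 50% split on a binary independent variable and 50% rate in the outcome for the reference group", and OR 1.22 per standard deviation of a continuous predictor.

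Section 11.3 then fixes seven predictors, each tested in its own model. Four are continuous. The other three are "practice region (categorical with six levels representing each PBRN region), practice location (binary with ubran/suburban vs rural") and "completion of residency program type (categorical, with three levels representing AEGD vs GPR vs none"). Categorical predictors are dummy coded, so region has five terms and residency two. Linear regression is planned for four items (2.IV, 3.IV, 7.IV, 8IV). All tests are adjusted by the Benjamini-Hochberg method.

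**The concern.** The power statement is offered for the tests in 11.3, but it describes simpler cases than some of those tests. A joint test of several dummy terms spreads the same R over more degrees of freedom and has less power than a one-term test. Calling the figure a multiple correlation invites its use for exactly those predictors. The odds ratio is given for an evenly split binary predictor, while the one binary predictor sets rural practices against all others.

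At stake is how results for region, residency and location are set against the design. A reader who takes the 80% at face value would credit the overall region test on the linear outcomes with more sensitivity to R = .10 than it has.

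**Working it through.** **Inputs.** From 11.2.1: N = 825, two-sided alpha .05, 80% power, R = .10, OR 1.48, 50% split, 50% reference outcome rate. From 11.3: 1 df for each continuous predictor and for location, 2 df for residency, 5 df for region. The rural share is not in the protocol and is varied below as an assumption.

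**Linear regression.** F test of R² with k numerator and N − k − 1 denominator df, and non-centrality λ = N·R²/(1 − R²). At R = .10, λ = 825 × .01/.99 = 8.33 for every k. Only the degrees of freedom and the critical value change.

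| Predictor | k | Critical F | Power at R = .10 | R detectable at 80% |
|---|---|---|---|---|
| single term | 1 | 3.85 | 82.2% | .097 |
| residency | 2 | 3.01 | 73.5% | .108 |
| region | 5 | 2.23 | 58.1% | .124 |

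The first row reproduces the protocol's figure, since .097 rounds to .10. The other two rows do not. Explained variance at the detectable R is 0.9%, 1.2% and 1.5%. For scale, 80% power at R = .10 would take about 957 respondents for residency and 1,276 for region.

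**Logistic regression, the protocol's own case.** With p1 = .50, p2 = 1.48/2.48 = .5968 and the difference is .0968. With 412.5 per group, the pooled proportion is .5484, the standard error under the null (pooled) is .03465 and under the alternative (unpooled) .03449. Power = Φ[(.0968 − 1.96 × .03465)/.03449] = Φ(.837) = 79.9%. The detectable OR is 1.481, so OR 1.48 is reproduced.

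**Logistic regression, unequal split.** Same formula and 50% reference rate, with group sizes 825 × (1 − share) and 825 × share. At a 20% rural share (660 and 165) the standard errors are .04349 and .04286, so power = Φ[(.0968 − 1.96 × .04349)/.04286] = Φ(.27) = 60.6%.

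| Assumed rural share | Power at OR 1.48 | OR detectable at 80% |
|---|---|---|
| 50% | 79.9% | 1.48 |
| 40% | 78.2% | 1.49 |
| 30% | 72.5% | 1.54 |
| 20% | 60.6% | 1.64 |
| 15% | 51.1% | 1.74 |
| 10% | 38.3% | 1.94 |

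**Continuous predictor, logistic.** Detectable OR per SD = exp[(1.96 + 0.84)/√(825 × .25)] = exp(.195) = 1.215, which agrees with the stated 1.22.

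**The case against.** The strongest reply is that nothing in 11.2.1 is miscalculated. Each figure reproduces in its simple case, and the odds ratio comes with its conditions attached. That is right for OR 1.48, and it is why that figure should stay. It does not rescue R = .10, which carries no condition on the number of terms and is introduced as covering the tests in 11.3.

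A reader might infer that the location test is badly underpowered. The documents do not support this as a fact, because no rural share is given. The loss is negligible at 40% rural and becomes large only at about 20% or less.

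A reader might also infer that region, residency and location all lack their stated power throughout. For logistic models, 11.2.1 claims nothing about multi-level predictors, so no stated figure is contradicted there. The contradiction for region and residency is confined to the four linear-regression items.

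Nor is the 50% reference rate a real fault. At a 50/50 split, power for OR 1.48 is still 79.8% at a 40% rate and 76.0% at 30%; it drops to 66% only near 20%, a rate the protocol does not suggest.

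Sections 3.2 and 11.1.2 word residency in a way that could be read as binary, but 11.3 sets three levels, and the point about region does not depend on this.

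Finally, the shift in detectable R is modest, these figures serve only secondary objective 1, and the protocol nowhere says that a non-significant result will be taken as no association. All of this stands, and it limits the point to a correction of wording.

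**Conclusion.** The point holds in two parts of unequal strength.

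- **R = .10.** This follows from the protocol's own inputs. The stated 80% power is met for single-term predictors (82%) but not for residency (about 73%) or region (about 58%). The detectable R is about .11 and .12 instead of .10. It rests on the joint test of the dummy terms in separate models.
- **OR 1.48.** The figure is correct as conditioned. What is missing is its link to the planned binary predictor. Depending on an assumed rural share of 40% down to 10%, the detectable OR runs from 1.49 to 1.94, with a 50% reference rate.

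All these values, the protocol's and those above, use unadjusted alpha .05. Benjamini-Hochberg never makes an individual test easier to pass, so they are best-case figures for the analysis as planned. At that alpha, R = .10 and OR 1.22 per SD stand for the four continuous predictors. The confidence-interval widths that support the primary objective and secondary objective 2 are not touched by this point. It gives no ground for a larger sample.

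**What to change.** In 11.2.1, item 2:

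1. State the detectable R by predictor: .10 for single-term predictors, .11 for residency (2 df) and .12 for region (5 df; .124 before rounding).
2. Keep OR 1.48 as the 50/50 case. Add the detectable OR at the rural share among eligible dentists in the enrollment database, which holds practice location (section 7.4).
3. Say that all power figures are at alpha .05 before the Benjamini-Hochberg adjustment in 11.3.

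The cost is a few lines of text and one tabulation of data the network already holds. Sample size, data collection and analyses stay as they are. The stated figures become somewhat less favourable.

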11.3 Final Analysis Plan

We will examine the distribution of all variables prior to analyses and verify all missing and out-of-range values. We will evaluate all inferential analyses at an alpha level of .05.

For the primary objective and secondary objective 2, we will use descriptive statistics for each of the items in the questionnaire and vignettes. Descriptive statistics will also be used for analysis for each of the practitioner and practice descriptors in the network's Enrollment Questionnaire database. We will also calculate confidence intervals around proportions for categorical items and around means for interval level items.

For secondary objective 1, we will use logistic regression for binary outcomes (items 11.I, 13.I, 14.I, 15.I, 16.I, and Vi1.7 & V1.8 [option a vs b-d]), ordinal logistic regression for ordinal outcomes (Vi1.7 & V1.8 [option b vs c vs d]), and linear regression for the reasonably continuous outcomes (2.IV, 3.IV, 7.IV, 8IV). For each regression analysis, we will test the following independent variables separately: practice region (categorical with six levels representing each PBRN region), practice location (binary with ubran/suburban vs rural), duration since graduating dental school (continuous), completion of residency program type (categorical, with three levels representing AEGD vs GPR vs none), number of patients seen in the past three months taking ACs (continuous), familiarity with DOACs (continuous), and number of patients seen in the past three months taking DOACs (continuous). Categorical independent variables will be dummy coded. Also, because of the large number of tests being conducted, we will adjust for multiplicity using the Benjamini and Hochberg method.³⁷

Missing data. Data from incomplete questionnaires may be included in data analyses. Participants will be able to submit questionnaire with incomplete data as 22 % (6/27) of the questions do not require responses. Depending on the extent of missing data and available resources for analyses, the study team may consider statistically appropriate methods for imputing missing information.

12 SOURCE DOCUMENTS AND ACCESS TO SOURCE DATA/DOCUMENTS

Source data/documents will be maintained by the NCC for this study. The NCC will program the electronic survey and vignettes into their electronic data capture (EDC) on the HUB website. Participants will be sent an email invitation with a direct link to the electronic survey and vignettes. After completion of the electronic survey, data will be collected and maintained through the EDC.

Only study personnel (i.e., the NCC, PI, and designated study team members) will have access to the data. All research computers and associated study documents will be password-protected and maintained in compliance with ICH E6, Section 4.9 and regulatory and institutional requirements for the protection of confidentiality of subjects. Study staff will permit authorized representatives of NIDCR and regulatory agencies to examine (and when required by applicable law, to copy) research records for the purposes of quality assurance reviews, audits, and evaluation of study safety, progress, and data validity.

The source documents for this study are:

- Electronic anticoagulants in dentistry questionnaire administered through the NCC EDC on the HUB website
- Data collected in the Network Enrollment Questionnaire

13 QUALITY CONTROL AND QUALITY ASSURANCE

For the quality control (QC) and quality assurance (QA) activities associated with data collection and processing, the NCC will develop a DQMP in which the specific data QA/QC procedures will be provided. These procedures will include the development of automatic data quality checks in the EDC for the questionnaire and processes related to data accuracy and completeness. The EDC will be programmed with edit checks and response limiters to reduce data response errors.

14 ETHICS/PROTECTION OF HUMAN SUBJECTS

14.1 Ethical Standard

The PI will ensure that this study is conducted in full conformity with the principles set forth in The Belmont Report: Ethical Principles and Guidelines for the Protection of Human Subjects of Research, as drafted by the US National Commission for the Protection of Human Subjects of Biomedical and Behavioral Research (April 18, 1979) and codified in 45 CFR Part 46 and/or the ICH E6.

14.2 Institutional Review Board

The protocol, informed consent form(s), recruitment materials, and all participant materials will be submitted to the National Dental PBRN Central Institutional Review Board (IRB) for review and approval. The UAB IRB for Human Use serves as the National Dental PBRN Central IRB. Approval of both the protocol and the consent form(s) must be obtained before any participant is enrolled. Any amendment to the protocol will require review and approval by the IRB before the changes are implemented in the study.

For those study investigators requiring IRB approval by their institutions, the study institution PI will submit for IRB approval and provide the Central IRB with the appropriate approved IRB documents.

